**Cessation Study**

This study will enroll at least 600 participants to address the primary aims.

*Primary Aim 1:* We computed power for the GLMM longitudinal analysis of abstinence outcomes using a SAS macro developed by Dang and colleagues with the following parameters:  $N=300$  per group; 3 time-points; drop-out rate of 20%; treatment marginal rates (over time) of 30% vs 40%; random effects variance=1; and within-subject correlation=0.6. Power for this scenario is 0.91. Thus, the proposed study appears to be powered adequately to yield a statistically significant group difference in point-prevalence abstinence in the longitudinal GLMM analyses.

“Breaking Addiction to Tobacco for Health (BREATHE) Study”

PI: [name], MPH, MBA; UW-CTRI Center Grant: 1P01CA180945-01.

Power analyses were also computed for 6-month point-prevalence abstinence using nQuery Version 7.0 (Statistical Solutions, Cork, Ireland). With sample sizes of Abstinence-Optimized Cessation Treatment=300, and Modern Usual Care=300 we examined the power to detect the primary outcome—biochemically confirmed 7-day point-prevalence abstinence at 6 months post-target quit day. A previous meta-analysis found that abstinence rates at 6 months post-quit were 23.4% of participants receiving 8 weeks of nicotine patch and 28.1% for those receiving quitline counseling and medication, as will occur in the M-UC treatment. Given that this will be an effectiveness trial with only 1 quitline call, we expect that M-UC will likely produce a lower 6-month abstinence rate of approximately 20%. With  $\alpha=.05$ , and  $n=300$  for M-UC and  $n=300$  for the AOCT, we are powered at .80 to detect a 10% difference in relapse rates of the AOCT vs. M-UC. Therefore, we are powered to detect approximately a 10% treatment effect, which we consider to be clinically meaningful.

*Primary Aim 2:* Power analyses for the main systems outcome were computed based on the approach described by Glick and implemented in STATA Version 12.1 (StataCorp, College Station, TX) programs developed by Glick (<http://www.uphs.upenn.edu/dgimhsr/stat-samps.htm>). For purposes of powering cost-effectiveness comparisons, we utilized net monetary benefit (NMB) which has benefits over the incremental cost-effectiveness ratio (ICER). In contrast to a ratio measure such as the ICER, NMB is a continuous measure with a relatively normal distribution; in addition, the variance for NMB is well-defined which permits good estimation of confidence intervals, sample size, and power. NMB is computed as the difference in effectiveness ( $\Delta Q$ ) minus the difference in costs divided by willingness to pay ( $\Delta C/W$ ). Willingness to pay ( $W$ ) is conceptualized here as the amount society would be willing to pay for a health benefit; for our purposes,  $W$  is the amount that would result in an additional quality-adjusted life year (QALY). Power was computed for two key comparisons: (1) cost-effectiveness of COT relative to UC, and (2) cost-effectiveness of AOT relative to UC. We made the following assumptions for each of these comparisons: sample size of  $n=300$  for the Abstinence-Optimized Cessation Treatment and  $n=300$  for the Modern Usual Care treatment; two-tailed test;  $\alpha=.05$ ; standard deviation (SD) for costs=250; SD for effects (i.e., abstinence rates)=.42; correlation for the difference in costs and effects=.1; and maximum willingness to pay=\$50,000. For the AOCT vs. M-UC comparison, we set the difference in abstinence effects at .1 (i.e., a 10 percentage point difference; 20% vs. 30%) and a cost difference at \$1222 reflecting a UC cost of \$128 and AOCT cost of \$1350. Power for this comparison is .60. However, we do have sufficient power (.80) to determine cost-effectiveness if there is a 12 percentage point difference in abstinence rates. This analysis requires a larger abstinence difference to establish that it is cost-effective, as well as clinically effective, because of the large cost differential.

*Secondary Aim:* Published estimates of sample sizes for mediational analyses, for various types of tests (e.g., the joint significance test and the Sobel test), provide the minimum sample size needed for detecting a mediated effect when the size of the effect of an independent variable ( $X$ ; e.g., medication effect) and the size of the mediator effect ( $M$ ; e.g., coping) are jointly considered. Based upon these values, if both the  $X$  effect and  $M$  effect are small/medium, a sample size of 196 would be needed to detect the mediated effect. Thus, we feel confident that our sample sizes of 270 per group ( $n$ 's=300 with 10% attrition) are sufficiently large to detect at least small/medium-sized (7.5% of variance) effects even in the presence of measurement error.

[figure not shown]
“Breaking Addiction to Tobacco for Health (BREATHE) Study”

PI: [name], MPH, MBA; UW-CTRI Center Grant: 1P01CA180945-01.

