**Cessation Study**

*Primary Aim 1:* A primary aim of Project 3 is to compare Abstinence-Optimized Cessation Treatment (AOCT) with Modern Usual Care (M-UC) on 7-day point-prevalence abstinence evaluated at 8, 16, 26, 39 and 52 weeks postquit. We will use GLMM implemented via SAS PROC GLIMMIX (SAS Institute Inc., Cary, North Carolina) to test the group effects in longitudinal models. Specifically, we hypothesize that participants receiving AOCT will have higher cessation rates at each timepoint than those receiving M-UC. We will also analyze other clinical outcomes because they provide complementary information about outcome (e.g., initial cessation, 6- and 12- month point-prevalence abstinence, latency to lapse and relapse, and treatment engagement and adherence) as recommended by SRNT Workgroup and others. We will evaluate initial cessation (did or did not establish 24 hours of abstinence in the first 2 weeks

“Breaking Addiction to Tobacco for Health (BREATHE) Study”

PI: [name], MPH, MBA; UW-CTRI Center Grant: 1P01CA180945-01.

following the quit day) and 6- and 12-month abstinence rates using logistic regression and latency to lapse and relapse using Cox proportional-hazards regression. We will also examine cessation outcomes controlling for treatment adherence in secondary analyses. The distributions of the adherence data (percentage of days using nicotine replacement; number of mini-lozenges used per day; percentage of counseling sessions completed) will be examined to inform decisions about transformation and analysis options.

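### Cessation Study, Primary Aim 1: the analysis plan tests a five-time-point longitudinal model, the power section calls CO-confirmed 6-month abstinence the primary outcome, and nothing ranks the two

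*Combined protocol and SAP*

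**What the plan says.** Analytic Plans, Cessation Study, Primary Aim 1, opens with "A primary aim of Project 3 is to compare Abstinence-Optimized Cessation Treatment (AOCT) with Modern Usual Care (M-UC"). The outcome it names for this comparison is "7-day point-prevalence abstinence evaluated at 8, 16, 26, 39 and 52 weeks postquit". The test is the group effect in a longitudinal GLMM. The hypothesis is that AOCT does better at every time point. The same paragraph continues: "We will also analyze other clinical outcomes because they provide complementary information about outcome". Its examples begin with "initial cessation, 6- and 12- month point-prevalence abstinence, latency to lapse and relapse", and the 6- and 12-month rates are assigned to logistic regression. The paragraph does not mention CO confirmation and does not use the term primary outcome.

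The power section, Cessation Study, Primary Aim 1, presents two calculations:

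- A GLMM calculation with 300 per group and "3 time-points; drop-out rate of 20%; treatment marginal rates (over time) of 30% vs 40" percent, giving power of 0.91.
- A single-time-point calculation, introduced with "we examined the power to detect the primary outcome—biochemically confirmed 7-day point-prevalence abstinence at 6 months post-target quit day". Its control rate is stated as "we expect that M-UC will likely produce a lower 6-month abstinence rate of approximately 20" percent, and it concludes "we are powered at .80 to detect a 10% difference in relapse rates of the AOCT vs. M-UC".

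The Cessation Study part of the Data Collection section uses the term primary outcome once more, but fixes only the product (combustible tobacco). It gives no time point, model or CO rule. Its list of key clinical outcomes includes 6- and 12-month continuous abstinence from all tobacco, which is a different construct.

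Table 12, the Table 5 footnote and the participant payment section place post-baseline CO testing at Week 26 only, among those who report abstinence.

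**The concern.** The same measure, 6-month point-prevalence abstinence, is complementary in the analysis plan and primary in the power section, under one aim. An analyst following the analysis plan would decide the aim on the GLMM; one following the power section would decide it on CO-confirmed Week 26 abstinence.

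The two are not the same endpoint under different names. Only Week 26 can carry CO confirmation, so the other four GLMM points rest on self-report, collected on the assessment-call schedule in the Data Collection text and Table 12. The design inputs differ as well: three time points at 30% vs 40% for one calculation, a single time point at 20% vs 30% for the other.

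If the tests split, the main efficacy conclusion of a 600-participant trial would depend on which section is taken to govern, and that could be settled after the results are known.

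**Working it through.** **1. The plan's own figure.** Inputs from the power section: 300 per arm, alpha .05, control 20%. The 10-point difference is spelled out as 20% vs 30% under Primary Aim 2. Sidedness is not stated for Aim 1; two-sided is assumed, as stated for Aim 2.

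- Pooled standard error: √(2 × .25 × .75 / 300) = .03536. Unpooled: √((.2 × .8 + .3 × .7) / 300) = .03512.
- Power = Φ((.10 − 1.96 × .03536) / .03512) = Φ(.874) = .81. The stated .80 reproduces.

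**2. How closely the two tests are linked.** Assume 300 per arm, no drop-out, equal rates over time and a within-person correlation r. Approximate the GLMM test by the generalised least-squares mean of the five time points. With exchangeable correlation, the correlation between that test and the Week 26 test is c = √((1 + 4r)/5):

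- r = .4: √.52 = .721
- r = .6: √.68 = .825
- r = .8: √.84 = .917

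The AR(1) equivalents are .607, .707 and .832.

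**3. How often they disagree at a constant 20% vs 30%.** The Week 26 statistic has mean .10/.03512 = 2.85, giving power .813 (unpooled). The five-point statistic has mean 2.85/c, giving exchangeable power .977, .932 and .874. From the bivariate normal distribution:

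| Structure, r | GLMM only | Week 26 only | Disagree |
|---|---|---|---|
| Exchangeable .4 | .167 | .003 | .170 |
| Exchangeable .6 | .129 | .009 | .138 |
| Exchangeable .8 | .077 | .015 | .093 |
| AR(1) .4 | .185 | .000 | .185 |
| AR(1) .6 | .171 | .003 | .173 |
| AR(1) .8 | .125 | .010 | .135 |

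Modelling CO-confirmed status separately, with an assumed 10% to 30% of self-reported Week 26 abstainers unconfirmed in both arms and exchangeable correlation, gives disagreement of 13% to 19%.

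**4. Direction if the effect fades.** AOCT medication runs to Week 26 and its maintenance calls to Week 22, so Weeks 39 and 52 fall after treatment. Take assumed differences of 10, 10, 10, 5 and 5 points; their mean is 40/5 = 8. With exchangeable r = .4/.6/.8 and equal weights, GLMM-only is .114/.058/.015 and Week-26-only is .035/.072/.116. If the weights also use the unequal variances, Week-26-only ranges from .04 to .20. Either way it exceeds GLMM-only at r = .6 and .8.

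**5. False-positive rate if either result could be claimed.** This is 1 − P(both |Z| < 1.96) under the null with correlation c: .082/.076/.069 (exchangeable) and .087/.083/.076 (AR(1)). With confirmed status modelled separately it is .074 to .089.

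**6. Three versus five time points.** At 30% vs 40%, with an assumed linear drop-out to 20% and exchangeable r = .4/.6/.8 on the observed scale, power is .900/.842/.785 with three points and .938/.870/.799 with five. The stated .91 is neither confirmed nor disputed, because the power section does not say on which scale its .6 correlation is defined.

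**The case against.** The best counter-argument is that only one complete endpoint is ever labelled the primary outcome, namely CO-confirmed abstinence at 6 months. The Week 26 CO visit and the 20% vs 30% used for Primary Aim 2 fit that reading. On this view the analysis plan merely supplies a model for the aim, its hypothesis covers every time point including Week 26, and its list of other outcomes does not name the CO-confirmed version. This shows which reading might have been intended. It does not settle the matter: the label appears only in a power calculation, while the section that specifies the test puts the 6-month measure among the complementary outcomes.

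Three stronger readings are tempting, and the documents do not support them:

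- **That the split would nearly always favour the GLMM.** This holds only for a constant effect and can reverse under modest fading. The disagreement figures also put 20% vs 30% into both tests, whereas the plan powers its GLMM at 30% vs 40%. With an assumed control profile of 50, 40, 20, 20, 20 (mean 150/5 = 30%), a constant 10-point effect and exchangeable r = .8, the split is .055 GLMM-only and .033 Week-26-only.
- **That the plan inflates its type I error.** It nowhere says that either result may count. The .07 to .09 is what such a rule would cost, not a property of the plan as written.
- **That the trial is too small.** The .80 reproduces, and using five time points instead of three slightly raises longitudinal power in the approximation above.

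**Conclusion.** The concern holds as an unresolved conflict over which test decides Primary Aim 1 of the Cessation Study. It is a contradiction between two sections under the same aim, not an arithmetic error.

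Its size is a chance of about 9% to 19% that the two candidate tests reach different conclusions. That range rests on 300 per arm, 20% vs 30% at all five points, no drop-out, and an assumed correlation of .4 to .8 (exchangeable or AR(1)). The direction of a split is left open because it depends on the effect after Week 26. The conflict itself is read from the text and depends on none of these assumptions.

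**What to change.** In Analytic Plans, Cessation Study, Primary Aim 1, name one primary outcome, time point, tobacco definition and test, and rank the other analysis as secondary. Bring the Data Collection and power sections into line. Either choice is acceptable.

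- **If CO-confirmed Week 26 abstinence is primary:** quote .80, not .91, as the primary power, and state how self-reported abstainers without a CO test are scored. The cost is a lower stated primary power.
- **If the GLMM is primary:** remove the primary-outcome label from the 6-month power calculation, say that the outcome is self-reported, and rerun the longitudinal power on the five planned time points instead of three. The cost is a primary result that rests mostly on self-report.

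The work is wording, plus one power rerun under the second choice. Sample size, visits and data collection stay as they are. The choice should be recorded before outcome data are analysed.

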*Primary Aim 2:* Another primary aim is to compare AOCT and M-UC on outcomes important to healthcare systems: net monetary benefit (NMB), incremental cost-effectiveness ratio (ICER), cost per long-term quit, and patient ratings of treatment and healthcare system quality. All of these will inform decision-making with regard to the efficient allocation of healthcare resources. Specifically, we hypothesize that, relative to M-UC, AOCT will produce an NMB higher than zero. Net monetary benefit analyses will convert the long-term relapse rates to Quality-Adjusted Life Years added (QALYs) and then monetize the QALYs added using a range of willingness to pay values. NMB analyses will allow us to compute confidence intervals and report whether these confidence intervals overlap for the AOCT relative to M-UC. For the ICER analyses, we will compare the additional cost of the AOCT to M-UC costs. Participants’ quality ratings will be analyzed using ANOVAs. We will examine the role of cessation success in satisfaction ratings and control for cessation success as needed.

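### The cost-effectiveness power for Primary Aim 2 of the Cessation Study sets a per-QALY threshold against raw abstinence rates, so the stated .60 and .80 hold only if each extra quit is worth exactly one QALY

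*Combined protocol and SAP*

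**What the plan says.** In the power section (Cessation Study, Primary Aim 2), net monetary benefit (NMB) is the difference in effectiveness minus the cost difference divided by W. The text says that W "is the amount that would result in an additional quality-adjusted life year (QALY"), and the inputs include "maximum willingness to pay=\$50,000". The effect inputs are abstinence figures: "SD for effects (i.e., abstinence rates)=.42; correlation for the difference in costs and effects=.1". For the comparison of AOCT with M-UC, "we set the difference in abstinence effects at .1 (i.e., a 10 percentage point difference; 20% vs. 30"%), with a cost difference of $1222 ($1350 less $128). The stated power is .60 at that difference and .80 at a 12-point difference.

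Under Analytic Plans (Cessation Study, Primary Aim 2), the NMB analyses "will convert the long-term relapse rates to Quality-Adjusted Life Years added (QALYs) and then monetize the QALYs added" over a range of willingness-to-pay values. The hypothesis is that AOCT will have an NMB above zero relative to M-UC.

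**The concern.** The two terms of the NMB formula must share a unit. Dollars divided by dollars per QALY gives QALYs, so the effectiveness term must also be in QALYs. The power calculation uses the proportion abstinent instead. The SD confirms this: a 0/1 variable has SD .40 at 20% and .46 at 30%, and .42 lies between them. The subtraction is coherent only if each additional quitter gains exactly one QALY. Neither the power section nor the analysis section says so, and no QALY-per-quit factor appears elsewhere in the documents.

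The factor does not cancel out. The cost term stays at 1222/50000 whatever a quit is worth, while the effect and its SD both scale with QALYs per quit. A small factor lets the cost term absorb most of the benefit, and a large one makes it negligible. What is at stake is the stated power for a primary aim, including the assurance that a 12-point difference is enough for .80.

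**Working it through.** **Inputs from the plan.** There are 300 participants per arm ("With sample sizes of Abstinence-Optimized Cessation Treatment=300, and Modern Usual Care=300" in the Primary Aim 1 power text, repeated for Primary Aim 2). The test is specified as "two-tailed test" at alpha .05. For costs, "standard deviation (SD) for costs=250" (dollars), and the cost difference is $1222. The SD of effects is .42, the correlation .1 and W $50,000. The abstinence difference d is .10 or .12.

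**Input not in the plan.** QALYs gained per quit, called q here. The range used below is an assumption.

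**Formulas.** With effect and SD both multiplied by q:

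- Incremental NMB divided by W: D = q·d − 1222/50000 = q·d − .02444
- SD of costs on the QALY scale: 250/50000 = .005
- SD = √[(.42q)² + .005² − 2(.1)(.42q)(.005)]
- SE = SD·√(2/300)
- Power = Φ(D/SE − 1.96)

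**Reproducing the plan's figures (q = 1).**

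- SD = √(.1764 + .000025 − .00042) = .4195, and SE = .4195 × .08165 = .03425
- 10 points: D = .10 − .02444 = .07556, z = 2.206, power = .597 (stated .60)
- 12 points: D = .12 − .02444 = .09556, z = 2.790, power = .797 (stated .80)

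Both match to rounding. A one-sided test gives .71 and .87, which does not match. Reversing the sign of the correlation gives .595 and .795, a negligible change. The stated figures therefore come from applying $50,000 directly to the abstinence difference.

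**Varying q, all other inputs as stated.** The difference needed for .80 is [(1.96 + .8416)·SE + .02444]/q.

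| QALYs per quit (assumed) | Power, 10 points | Power, 12 points | Difference needed for .80 |
|---|---|---|---|
| 0.5 | .32 | .55 | 14.5 points |
| 0.75 | .50 | .72 | 12.9 points |
| 1 (implied by the plan) | .60 | .80 | 12.0 points |
| 1.5 | .69 | .86 | 11.2 points |
| 2 | .73 | .88 | 10.8 points |
| 3 | .76 | .90 | 10.4 points |

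Worked example at q = 0.5 and 10 points: D = .05 − .02444 = .02556; SD = √(.0441 + .000025 − .00021) = .2096; SE = .01711; z = 1.494; power = .32.

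**Limits.** Incremental NMB is zero at q = .02444/.10 = 0.244 for a 10-point difference and q = .02444/.12 = 0.204 for 12 points. Just above the first of these, at q = 0.25, power at 10 points is about .03. With negligible cost, the ceiling is about .83 at 10 points and .94 at 12. At q = 5, power at 10 points is still .79.

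**The case against.** The strongest reply is that nothing is miscalculated. The arithmetic is right for its inputs, one QALY per quit may be a deliberate simplification, and if the true value is higher the stated power is conservative. It is correct that the arithmetic is sound and that the direction is unknown. But the simplification is not declared, so a reader cannot tell that the factor was set to one, and the documents give no ground for placing it at or above one.

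A second reply is that the plan already admits low power: .60 at the design difference, which it attributes to the cost gap. That warning survives, since 10-point power stays below .80 for every q up to 5. The assurance at 12 points does not survive for q below 1.

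Third, the very low figures arise near break-even, where the true benefit is close to zero and no sample size would help. The .03 at q = 0.25 also counts only rejections in AOCT's favour; counting both tails, the rejection rate is about .05. This is fair, and the case does not depend on that extreme: 0.5 to 3 QALYs per quit already gives .32 to .76 at 10 points and .55 to .90 at 12.

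Finally, in this formula power depends on q and W only through their product (q = 2 at $50,000 equals q = 1 at $100,000), and the analysis will vary W. That explores the same sensitivity in the results, but it does not repair a power figure quoted for a single W with an unstated q.

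**Conclusion.** The concern holds. The fault is a mismatch of units, not a slip in calculation: W is in dollars per QALY, while the effect and its SD are in quits. The stated .60 and .80 describe the planned QALY-based analysis only at one QALY per quit. Below one QALY they are too high and above it too low. The 12-point requirement becomes 14.5 points at 0.5 QALY and 10.8 points at 2 QALYs.

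No single corrected figure can be given, because the documents contain no conversion factor; the range used here is assumed. The calculation also treats the gain as constant per quit. Variation in QALYs between quitters, or uncertainty in the conversion, would lower power further. The abstinence comparison in Primary Aim 1 is unaffected.

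**What to change.** There are two ways to put this right.

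1. State the QALYs-per-quit factor that the analysis will use, with its source and plausible range. Multiply both the abstinence difference and its SD by it, and restate power and the difference needed for .80 as ranges over that factor and the planned willingness-to-pay values.
2. If cost per long-term quit was intended (it is also listed as a Primary Aim 2 outcome), relabel W in the power section as $50,000 per additional long-term quit. Say that .60 and .80 apply to that measure and not to the QALY-based NMB.

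The first is preferable because it describes the analysis actually planned. Either costs a recalculation or a relabelling and a few sentences, with no change to design or data collection. The drawback of the first is that one figure becomes a range, which may be less favourable.
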